#### **Step 7: Publication**

Data is analyzed and presented as statistical data in a peer reviewed journal. Data from Phase I may be published before Phase II is started.

#### Data structure

The tables below lay out the general data structure. Data may be structured in the following format but will not be limited to this structure.

Table 1: Clinical characteristics and outcomes

Clinical characteristics	All (N =)	Standard Arm	Experimental arm
Age, years (median, IQR)			
PSA (ng/ml) (median, IQR)			
DRE abnormal (N, %)			
Family history of prostate cancer (N, %)			
Previous negative prostate biopsy (N, %)			
Stockholm3 (median, IQR)			
Underwent MRI (N, %)			
PIRADS ≥3 (N, %) PIRADS ≥4 (N, %)			
Benign biopsy (N, %)			
ISUP 1 Prostate Cancer (N, %)			
ISUP ≥2 Prostate Cancer (N, %)			
ISUP ≥3 Prostate Cancer (N, %)			

# **Project description, Phase II**

#### Step 1: Recruitment, consent, and blood sampling

Men with no previous prostate cancer diagnosis, eligible for prostate cancer testing according to standard of care and meeting the study inclusion/exclusion criteria, will be offered to participate in the study. The physicians at participating primary care centers will offer the men participating in the study and inform that the patient will be randomized to either a control arm with PSA or an experimental arm with PSA and Stockholm3 done as reflex test if PSA  $\geq$  1.5 ng/ml.

Men that are interested and have read the *Research Participant Information* will sign an informed consent. Men that are not interested to participate in the study will be offered standard of care.

The physician orders "PSA+" from Unilabs' catalog. The analysis code for the test generates orders for two analyses: a standard PSA test and the Stockholm3 test. The research participant proceeds to the sampling unit, where three blood samples are collected: one

serum tube for PSA and two EDTA tubes for Stockholm3. All samples are transported to Unilabs in Solna/Huvudsta.

In parallel, the randomization is conducted in Unilabs' system. Each referral is randomly assigned to either the control arm (PSA diagnostics) or the experimental arm (Stockholm3 diagnostics).

# Step 2: Lab analysis

Samples are received at Unilabs in Solna/Huvudsta. Referrals assigned to the control arm are processed as follows:

- 1. The EDTA samples are discarded
- 2. The serum sample proceeds to PSA analysis
- 3. The PSA result is reported to the ordering physician

Referrals assigned to the experimental arm are processed as follows:

- 1. The serum sample is discarded
- 2. The EDTA samples proceed to Stockholm3 analysis
- 3. The Stockholm3 result is reported to the ordering physician

# Step 3: Clinical decision based on lab results

The man is referred to MRI by the primary care physician if  $PSA \ge 3$  ng/ml or if  $Stockholm3 \ge 11$ . Men with positive MRI (PIRADS  $\ge 3$ ) will be offered prostate biopsy.

#### **Step 4: Data collection**

See "Step 4: Data collection, Phase I" above.

# Step 5: Statistical analysis

Primary outcomes:

We will use a generalized linear model (GLM) with a log-link function and binomial
distribution test to for differences in detection rates of csPC. Results will be
presented as risk ratios (RRs) or risk differences (RDs) with corresponding confidence
intervals, adjusting for randomization stratification variables. In the event of
convergence issues, a modified Poisson regression model with robust standard errors
will be used as a backup strategy.

Superiority testing will be conducted to assess whether the Stockholm3-based diagnostic pathway detects a significantly higher number of clinically significant prostate cancers (csPC) compared to the standard PSA-based pathway. The null hypothesis ( $H_0$ ) assumes that both diagnostic strategies have equal detection rates,

whereas the alternative hypothesis ( $H_1$ ) assumes that the Stockholm3 pathway results in a higher detection rate. 95% confidence intervals for effect size estimates will be reported.

- Socioeconomic status (CNI, Care Need Index) of the participating site's catchment area (low, medium, high)
- Annual PSA testing volume at the participating site (low, medium, high)

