#### Phase II

The sample size is based on a superiority trial design to detect a 20% increase in csPC detection (4% in the control arm vs. 4.8% in the experimental arm). With a 5% significance level, 80% power, and a 1:1 randomized design, the required sample size is 10,856 participants per group (adjusted for 5% dropout), totalling 21,712 participants.

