# Phase I

Participating primary care unit will be 1:1 cluster randomized at study start to one of two study arms:

- Control arm: standard of care with PSA-based diagnostics
- Experimental arm: Reflex testing to Stockholm3 if PSA ≥1.5 ng/ml

To ensure balanced allocation between study arms, stratified block randomization is employed with strata defined by:

- Socioeconomic status (CNI, Care Need Index) of the participating site's catchment area (low, medium, high)
- Annual PSA testing volume at the participating site (low, medium, high)

Primary care units are identified and randomly assigned to a study arm using a centralized, computer-generated randomization list. The randomization is performed by an independent statistician who is not involved in the recruitment process.

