#### Phase II

Each referral is automatically assigned a referral identity number (RID) by the laboratory consisting of 8 digits. If the sum of numbers in the RID is even, the man is randomized to the control arm, if the sum of numbers in the RID is odd the man is randomized to the experimental arm. Given that RIDs are assigned consecutively by the laboratory for all the analyses in Sweden, the sum of numbers in the RID will be 50% odd and 50% even.

Study participants will be followed up at 2, 4 and 6 years following the recruitment.

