#### Secondary outcomes:

- Logistic regression models for compliance assessment
- Descriptive statistics for MRI and biopsy rates
- Detection of clinically significant prostate cancer at different PSA ranges
- Operating characteristics of PSA and Stockholm3 to predict csPC at different PSA and Stockholm3 cut-offs
- Operating characteristics of PSA and Stockholm3 to predict abnormal MRI (defined as PIRADS ≥3) at different PSA and Stockholm3 cut-offs
- Operating characteristics of PSA and Stockholm3 to predict abnormal MRI (defined as MRI that led to csPC) at different PSA and Stockholm3 cut-offs
- Unnecessary biopsies/MRIs: a normal MRI based on prostate imaging reporting and data system (PIRADS) (I.e. PIRADS 1, 2 and without lesion), benign pathology on biopsy, or low grade ISUP 1 cancer (aka, Grade Group 1, Gleason Score 3+3, Gleason Score 6)
- Adjusted analyses based on potential confounders (e.g., age, PSA levels)
- Healthcare utilization of resources (#MRI, #Biopsy, #ISUP grade group 1 cancers detected)
- Cox model for longer-term endpoints (prostate cancer specific mortality and overall mortality)

Randomization stratification factors will be included as covariates in the regression models used for analysis. Data analysis will be performed by the PI or key research personnel. An independent Data Analysis Committee headed by [name] will be overseeing the data analysis.

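### The Phase II primary model adjusts for stratification variables that Phase II does not have, and leaves individual baseline covariates out

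*Protocol*

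**What the plan says.** All references are to the protocol.

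- **Primary model.** Project description, Phase II, Step 5 specifies a log-link binomial GLM, with modified Poisson regression as backup. The effect is given as a risk ratio or risk difference "adjusting for randomization stratification variables. In the event of" convergence problems. The section ends by listing Care Need Index (CNI) and annual PSA testing volume of the site.
- **Secondary outcomes in the same step.** The rule is repeated for all regression models: "Randomization stratification factors will be included as covariates in the regression models used for analysis". Separately, the list includes "Adjusted analyses based on potential confounders (e.g., age, PSA levels").
- **Phase II allocation.** Randomization procedure, Phase II works on single referrals: "If the sum of numbers in the RID is even, the man is randomized to the control arm", and an odd sum leads to the experimental arm. No strata are mentioned.
- **Phase I allocation.** Only here, for primary care units, does the protocol say that "stratified block randomization is employed with strata defined by" CNI and PSA testing volume.
- **Data available.** The Data Collection table marks age, family history, 5-alpha reductase inhibitor use, earlier negative biopsy, digital rectal examination (DRE) and PSA as collected in both Phase II arms.
- **Specimens.** Phase II, Step 2 analyses serum and discards EDTA in the control arm. In the experimental arm it discards serum and analyses EDTA.

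**The concern.** The protocol fixes a covariate rule for the Phase II primary analysis by pointing to a feature that the Phase II design lacks. Whoever writes or checks the analysis cannot tell whether the two site-level factors are intended or were copied from Phase I.

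The rule also points to the less useful covariates. CNI category and testing volume describe a primary care unit and can be expected to say little about whether a particular man has csPC. In an individually randomized trial the main reason to adjust is precision, and that argues for individual prognostic factors in the primary model. The protocol collects such factors but places age and PSA adjustment among the secondary analyses, labelled as confounder control. What is at stake is a clear primary analysis and a modest amount of precision, not validity.

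**Working it through.** **1. The protocol's own figure.** Study size and outcome, Phase II plans to "detect a 20% increase in csPC detection (4% in the control arm vs. 4.8% in the experimental arm"). The test level is 5%, the power 80% and allocation equal. The result given there is that "the required sample size is 10,856 participants per group (adjusted for 5% dropout), totalling 21,712 participants".

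- Formula (unpooled, two-sided): n = (1.960 + 0.842)² × [0.04×0.96 + 0.048×0.952] / 0.008² = 10,313.4.
- Dropout: 10,313.4 / 0.95 = 10,856.2, which matches the stated 10,856 per group.
- Evaluable: 10,856 × 0.95 = 10,313 per arm, with unadjusted power 80.0%.

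**2. Strata, side by side.**

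| | Phase I | Phase II |
|---|---|---|
| Unit allocated | primary care unit | single referral |
| Mechanism | stratified blocks | digit-sum parity |
| Strata | CNI, PSA volume | none |
| Covariates in primary model | stratification variables (CNI, PSA volume) | the same wording and the same two factors |

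The last cell contradicts the one above it.

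**3. Gain from non-PSA baseline covariates.** The document gives no prognostic strengths, so these are assumptions. Modified Poisson simulations with age, family history and DRE (three assumed strengths, 120 trials each, so approximate) gave gains in effective sample size g of 1.1%, 3.2% and 7.1%. Power = Φ(2.802 × √(1+g) − 1.960):

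- g = 1.1%: 80.4%
- g = 3.2%: 81.2%
- g = 7.1%: 82.6%

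The gain is therefore 0.4 to 2.6 points.

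**4. What PSA band could add.** Assumptions not in the document: bands <1.5, 1.5 to <3 and ≥3; csPC found only at PSA ≥ 3 in the control arm and only at ≥ 1.5 in the experimental arm; 20-35% of experimental-arm csPC in the middle band. With band shares q and band risks pE, pC:

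- Crude variance of log RR × n = 0.952/0.048 + 0.96/0.04 = 43.83, giving power 79.9% on this scale.
- Standardised variance × n = Σq·pE(1−pE)/0.048² + Σq·pC(1−pC)/0.04² + ½·Var(pE/0.048 − pC/0.04).
- Example: shares 65/25/10%, 20% of experimental csPC in the middle band. Then pC = 0.40 in the top band, and pE = 0.0384 (middle) and 0.384 (top). The sum is 14.27 + 15.00 + 0.28 = 29.55, ratio 0.674, power 92.6%.

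| Assumed share with PSA ≥ 3 | Power | Gain (points) |
|---|---|---|
| 10% | 90.6-92.6% | 10.7-12.7 |
| 15% | 86.5-87.9% | 6.7-8.1 |
| 20% | 84.5-85.5% | 4.6-5.6 |
| 25% | 83.2-84.0% | 3.3-4.1 |
| 30% | 82.4-83.0% | 2.5-3.2 |

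The functional form matters. In simulation, one linear log-PSA term in the log-link model gave 75.6-80.0% power, against 79.6-79.8% unadjusted.

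**5. Why PSA cannot simply be added.** Suppose the experimental arm's PSA reads 5% higher because of the specimen, while detection stays at 4.0% versus 4.8%. Assume log-normal PSA with 40% of men ≥ 1.5 and 15% ≥ 3, and that the experimental arm keeps 90% of the csPC the control arm finds at ≥ 3. Risks are then 0.2667 (control, top band), 0.24 (experimental, top) and 0.048 (experimental, middle).

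- Recorded experimental-arm shares become 16.32% (top) and 25.82% (middle), with risks 0.2244 and 0.0440.
- Pooled shares are 15.66% and 25.41%.
- Standardised RR = (0.1566×0.2244 + 0.2541×0.0440) / (0.1566×0.2667) = 0.0463/0.0418 = 1.11.
- For a reading 5% lower, the same steps give 0.0498/0.0383 = 1.30.

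The crude RR stays 1.20. Repeating this with 30-50% of men ≥ 1.5, 10-20% ≥ 3 and 80-100% kept gives about 1.04-1.17 for a high reading and 1.24-1.40 for a low one. Uniform risk within bands probably overstates the effect.

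**The case against.** The strongest reply is that this is a labelling slip. Both covariates are named, known before allocation and harmless to include, so the model can be fitted as written. Choosing prognostic covariates is usually left to the SAP, which is not shown. The stated size reproduces with 80.0% power, so nothing is underpowered on the protocol's own inputs. The secondary analyses already include csPC detection by PSA range and analyses adjusted for age and PSA.

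Most of this stands and limits the point. It does not remove it: the protocol itself sets the covariate rule for the primary analysis, and that rule contradicts its own allocation section. A later SAP would have to depart from the rule or repeat the error.

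A reader might infer something stronger: that the trial gives up 5 to 13 points of power at almost no cost by not adjusting for PSA. The document does not support this, for four reasons.

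- That range needs an assumed 10-20% of men with PSA ≥ 3. Men are selected by their physician, no PSA distribution is given, and at 25-30% the gain is about 2.5 to 4 points.
- PSA is assayed after allocation, from serum in one arm and necessarily from EDTA in the other. No comparability data are given, so adjustment could bias an otherwise unbiased comparison.
- Using one specimen type would change laboratory handling of tubes that are now discarded. That is more than a wording change.
- The zero-event bands are an idealisation. The referral rule says who must be referred; it does not exclude MRI in other men.

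**Conclusion.** The carry-over is established from the document alone: Phase II has no randomization strata, yet its primary model and its secondary regressions are said to adjust for them. It is also established that individual baseline covariates collected in both arms are absent from the primary model.

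The consequence is modest. Adjusting for non-PSA covariates would bring about 0.4 to 2.6 points of power, under assumed covariate strengths and from small simulations. The larger gain from PSA band, about 2.5 to 13 points for an assumed 10-30% of men with PSA ≥ 3, is not safely available under the present specimen handling. Leaving PSA out of the primary model is therefore defensible for now. The planned trial is neither underpowered on its own inputs nor invalid. The primary analysis should be corrected before Phase II starts.

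**What to change.** In Project description, Phase II, Step 5:

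- Remove the reference to randomization stratification variables from the primary and secondary outcome text. CNI and PSA testing volume may stay as ordinary site-level covariates, named as such.
- Pre-specify adjustment of the primary csPC comparison for age, family history, 5-alpha reductase inhibitor use and earlier negative biopsy. Add DRE only if it is recorded before the test result is known.
- Report a marginal risk ratio or risk difference with its 95% confidence interval, and keep the unadjusted ratio as a sensitivity analysis.
- State how values recorded as not known are handled, for example as a separate category.
- Keep PSA-band results secondary unless PSA comes from comparable specimens in both arms. If that is shown, standardise over bands; a single linear log-PSA term is not a substitute.

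The cost is wording, slightly more analysis work and a rule for the not-known values. No extra men, visits or samples are needed for the non-PSA part.

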#### Secondary outcomes:

- Logistic regression models for compliance assessment
- Descriptive statistics for MRI and biopsy rates
- Detection of clinically significant prostate cancer at different PSA ranges
- Operating characteristics of PSA and Stockholm3 to predict csPC at different PSA and Stockholm3 cut-offs
- Operating characteristics of PSA and Stockholm3 to predict abnormal MRI (defined as PIRADS ≥3) at different PSA and Stockholm3 cut-offs
- Operating characteristics of PSA and Stockholm3 to predict abnormal MRI (defined as MRI that led to csPC) at different PSA and Stockholm3 cut-offs
- Unnecessary biopsies/MRIs: a normal MRI based on prostate imaging reporting and data system (PIRADS) (I.e. PIRADS 1, 2 and without lesion), benign pathology on biopsy, or low grade ISUP 1 cancer (aka, Grade Group 1, Gleason Score 3+3, Gleason Score 6)
- Adjusted analyses based on potential confounders (e.g., age, PSA levels)
- Healthcare utilization of resources (#MRI, #Biopsy, #ISUP grade group 1 cancers detected)
- Cox model for longer-term endpoints (prostate cancer specific mortality and overall mortality)

Randomization stratification factors will be included as covariates in the regression models used for analysis. Data analysis will be performed by the PI or key research personnel. An independent Data Analysis Committee headed by [name] will be overseeing the data analysis.

#### **Step 6: Publication**

See "Step 6: Publication, Phase I" above.

#### Data structure

See "Data structure, Phase I" above.

#### **Ethical considerations**

Cluster randomization presents ethical challenges regarding the principles of justice and individual autonomy. Since entire primary care units are assigned to either the control or experimental arm, some patients will not have the opportunity to receive the experimental intervention, which they may perceive as a disadvantage. However, since the standard of care remains unchanged – meaning these patients would not have had access to the experimental intervention outside the study either – we do not consider this a major ethical concern.

There is a minimal risk of complications associated with the venous blood sampling, but since it is performed by highly experienced nurses, involves only a small amount of blood (15 ml), we do not believe there is a significant risk of physical discomfort.

A key ethical consideration in diagnostic studies is the risk of false negatives and false positives. False negatives may lead to delayed cancer detection and treatment, while false positives can cause unnecessary anxiety, invasive procedures, and potential complications. The experimental arm, by integrating Stockholm3 as a reflex test, is expected to reduce both false negatives – by detecting clinically significant prostate cancers at lower PSA levels – and false positives, by decreasing unnecessary MRI, thereby improving both patient safety and resource utilization.

All project data and test results will be kept anonymous on the encrypted and password protected database and will be analyzed with secure research designated computers at Karolinska Institutet to prevent unauthorized access to them. All researchers connected to the project are under confidentiality agreements. Results from the study will be presented in such a way that no individual information will be disclosed.

# **Approval**

The project will seek approval from the Swedish Ethical Review Authority (Etikprövnings-myndigheten). Written informed consent will be obtained from all participants before enrollment.

# **Timeline**

The study will start as soon as the project has received approval from the Swedish Ethical Review Authority. The target starting time is April 2025. The study is expected to be running until June 2026. The key connecting data to individuals will be discarded 10 years after the study ends.

# Study budget

The study budget will be covered by a grant from A3P Biomedical.

# **Participating healthcare providers**

Primary care providers in Sweden with laboratory services provided by Unilabs.

